Elvitegravir (EVG) Cerebrospinal Fluid (CSF) Pharmacokinetics in HIV-Infected Adults

Investigators:

[name] [name], PhD

Clinical Trials Identifier:

NCT02251236

Last Update:

2 July 2014

UCSD Human Research Protections Program New Biomedical Application RESEARCH PLAN

Instructions for completing the Research Plan are available on the HRPP website. The headings on this set of instructions correspond to the headings of the Research Plan. General Instructions: Enter a response for all topic headings. Enter "Not Applicable" rather than leaving an item blank if the item does not apply to this project.

Version date: 9/30/2013

PROJECT TITLE

Elvitegravir (EVG) Cerebrospinal Fluid (CSF) Pharmacokinetics in HIV-Infected Individuals

PRINCIPAL INVESTIGATOR

[name]. Professor of Medicine University of California, San Diego

FACILIZIES ir (EVG) Cerebrospinal Fluid (CSF) Pharmacokinetics in HIV-Infected Individuals

The study will be conducted locally at the UCSD AntiViral Research Center (AVRC), [name] and the HIV Neurobehavioral Research Program (HNRP), [name].

Document Date: 7/2/2014

ESTIMATED DURATION OF THE STUDY

The enrollment period is anticipated to be approximately 18 months with final results approximately 24 months after study initiation. Subject participation will be approximately 24 weeks.

5. LAY LANGUAGE SUMMARY OR SYNOPSIS (no more than one paragraph)

The proposed project is a single dose, single arm, open-label, multicenter, phase IV pharmacokinetic study with the primary aim of describing cerebrospinal fluid (CSF) concentrations of elvitegravir (EVG), an HIV integrase inhibitor. Stribild is an FDA-approved, multiclass combination drug with potent antiretroviral activity against HIV-1. Stribild is a tablet containing four drugs, one of which is EVG. The study population will be HIV-1 infected study subjects who are naive to EVG. The study will enroll 14 subjects at three sites in the United States, who will be given Stribild over a period of approximately six months. Blood draws, urine collection and lumbar punctures will be performed after screening, to generate 22 on-treatment CSF-blood specimen pairs. Pharmacokinetic (PK) analysis will provide a small-sample estimate of distribution of EVG into CSF. HIV Dementia Scale scores will also be measured. The study will recruit approximately 7 subjects at UCSD.

SPECIFIC AIMS 6.

Primary:

1) To describe the CSF concentrations of elvitegravir (EVG).

Secondary:

- 1) To determine the effects of Stribild on HIV RNA levels in CSF.
- 2) To evaluate the effects of Stribild on blood-brain barrier permeability as estimated by the CSF-to-serum albumin ratio.
- 3) To determine the effects of Stribild on HIV Dementia Scale scores.

7. **BACKGROUND AND SIGNIFICANCE**

7. BACKGROUND AND SIGNIFICANCE

StribildTM (elvitegravir/cobicistat/emtricitabine/tenofovir) was approved by U.S. Food and Drug Administration (FDA) in August 2012 as a new multiclass combination drug with potent antiretroviral activity against HIV-1.1

Two randomized double-blind phase III clinical trials have demonstrated the non-inferiority as well as the tolerability and safety of StribildTM compared to AtriplaTM and ritonavir-boosted atazanavir plus TruvadaTM. 2.3 Similar results have been found between ritonavir-boosted elvitegravir and raltegravir in treatment-experienced patients. 4 The safety assessment of StribildTM based on the pooled data from two comparable clinical trials with a total of 701 subjects in the StribildTM arms suggested that it distributes into the central nervous system (CNS) because 11-12% of participants reported relevant adverse events, such as somnolence, headache, dizziness, insomnia, or abnormal dreams. 5

HIV-associated neurocognitive disorder (HAND) is a common disease complication and is thought to be due to neurotoxic events that result from HIV replication in perivascular macrophages and microglia and immune and glial activation. Most data have supported the notion that antiretroviral regimens possessing better estimated distribution into the CNS result in more favorable neurologic and cognitive outcomes. The CNS penetration effectiveness (CPE) score is one approach that estimates a drug's effectiveness in the CNS. CPE values range from 1 (below average) to 4 (much above average) and raltegravir, an integrase strand transfer inhibitor, has an above average CPE value of 3. Higher CPE values are associated with lower CSF viral loads, better neurocognitive function, and better survival, although some studies have had inconsistent findings. Prior studies have reported significantly higher concentrations of raltegravir in CSF than the 50% inhibitory concentration for wild-type HIV-1, suggesting that raltegravir—and perhaps other integrase inhibitors—reach therapeutic concentrations in the brain.

During suppressive ART, persistent systemic and neuro-inflammation appears to be associated with HAND. HIV injures gut-associated lymphoid tissue early in the course of HIV disease, leading to translocation of microbial products, such as elevated plasma bacterial lipopolysaccharide (LPS) into blood. LPS binds to CD14 and can result in activation of myeloid cells. Higher soluble CD14 concentrations in blood are associated with HAND. Other soluble CSF and blood biomarkers reflecting monocyte activation (e.g., MCP-1) and inflammation (e.g., IL-6) have also been linked to HAND. HAND has also been associated with cardiovascular disease biomarkers such as soluble vascular adhesion molecule-1 (sVCAM-1). This may be important since switching to an integrase inhibitor, raltegravir, was associated with decreased inflammation- and cardiovascular disease-associated biomarkers, suggesting that these processes may be responsive to elvitegravir. 14

8. PROGRESS REPORT

Not Applicable.

9. RESEARCH DESIGN AND METHODS

The proposed project is a single dose, single arm, open-label, multicenter, phase IV pharmacokinetic study. This study plans to enroll 7 HIV-infected, EVG Naïve subjects at our site and 14 at all sites.

The goals of the study are to (1) describe the population pharmacokinetics of elvitegravir in CSF, and (2) determine the impact of StribildTM on suppressing HIV RNA in CSF, blood-brain barrier permeability, and HIV Dementia Scale scores. No published studies have addressed the following questions: 1) What are the concentrations of elvitegravir in the CSF in patients with HIV-1 disease? 2) Do these concentrations exceed the 95% inhibitory concentration (IC95) for wild-type HIV-1? 3) How does StribildTM affect blood-brain barrier permeability and HIV Dementia Scale scores? We will address these questions in a prospective, open-label treatment trial of HIV-infected, treatment-naive patients.

Even though this is primarily a pharmacokinetic study of FDA-approved drugs, adverse events will likely occur. According to the package insert, the most common adverse reactions are nausea (16%), diarrhea (12%), abnormal dreams (9%), headache (7%), fatigue (4%), rash (3%), insomnia (3%), and dizziness (3%).

Laboratory abnormalities can also occur, including elevations in creatine kinase (7%), elevated amylase (3%), and hematuria (3%). Serious adverse events, including lactic acidosis and severe hepatomegaly, have been reported but are uncommon. The standard regimen of StribildTM will be used. If a regimen change occurs during the course of the project, participation will be discontinued. Patients will be carefully screened and those with pre-conditions, such as morbid obesity or hepatitis B virus co-infection, will be excluded.

HIV-1 infected patients who are willing to initiation antiretroviral therapy and who are naive to the components of StribildTM will be the study population. StribildTM has been recently added into the DHHS Guidelines as an option for the first-line therapy. The study will enroll 14 subjects to generate 22 on-treatment CSF-blood specimen pairs, which is sufficient to provide a small-sample estimate of distribution of EVG into CSF. A tabular schedule of assessments is provided below.

Assessment	Screening	Baseline	Week 2	Week 8	Week 16	Week 24
Time window (days)	-28 to -1	0	12-20	49-63	105-119	161-175
Informed consent	X					
Brief assessment	X		X			
Eligibility assessment	X					
Full assessment		X				X
Telephone assessment				X	X	
HIV RNA, Plasma	X	X	X			X
CD4+ T-cell count	X		X			X
Drug resistance testing	X					
HIV RNA, CSF		X	X			X
HIV Dementia Scale		X				X
Study drug dispensing		X	X	X	X	X
Safety assessment			X			X
PK assessment			X			X

Signs and symptoms, laboratory results, and toxicities \geq Grade 2 will be recorded on the appropriate case report forms (CRFs).

Screening and Entry Evaluations

1) Screening Evaluations will occur within 28 days of study entry

- a) Details of the study will be carefully discussed with subjects during screening and the subject asked to read and sign an informed consent approved by the IRB at the participating institutions.
- b) Documented presence of HIV infection, as specified in Section 3.1.1 of the master protocol, prior to study entry.
- c) A brief medical history will be obtained and will include:
 - i) Previous diagnoses including liver disease, renal disease, fracture, osteoporosis, allergies, drug reactions, and most recent menses.
 - ii) Current prescription and non-prescription medications taken within 14 days prior to entry.
 - iii) Recent use of drugs of abuse or unprotected sexual contacts. Past use of needles.
 - iv) A signs-and-symptoms assessment, including: vital signs, height, and weight. Vital signs will include temperature, blood pressure, and pulse rate.

- d) 35 mL of blood and 15 mL of urine will be collected using standard methods.
- 2) The following laboratory tests must be performed within 28 days prior to study entry, unless otherwise noted:
- a) Hematology: hemoglobin, hematocrit, mean corpuscular volume (MCV), white blood cell count, differential white blood cell count, and platelet count.
- b) Blood chemistries: electrolytes, blood urea nitrogen (BUN), creatinine, glucose, phosphorus, and calcium.
- c) Liver function tests: total bilirubin, AST, ALT, alkaline phosphatase, and albumin.
- d) Coagulation: prothrombin time, international normalized ratio, partial thromboplastin time
- e) Urinalysis, including urine glucose and protein
- f) Estimated glomerular filtration rate (eGFR)
- g) For women of childbearing potential: Serum or urine pregnancy test.
- h) HIV RNA in blood plasma
- i) Lymphocyte subsets in blood (including CD4+ and CD8+ T-cell absolute counts and percentages)
- j) Hepatitis C and hepatitis B serologic testing
- k) Rapid plasmin reagent (RPR)
- 1) Drug resistance mutation genotyping in blood
- m) 5 mL of blood plasma will be stored at -80C.
- 3) Baseline (Entry) Evaluation: Within 28 days of the screening evaluation, eligible and consenting subjects will enter the study. Additional assessments will be performed and study drug will be dispensed.
- a) A complete medical history and physical examination will be performed:
 - i) Prior diagnoses including liver disease, renal disease, fracture, osteoporosis, allergies, drug reactions, and most recent menses.
 - ii) Current symptoms including those of an active systemic illness (e.g., fever) and bleeding or easy bruising.
 - iii) Prescription and non-prescription medications taken within 14 days prior to entry.
 - iv) Vital signs, including temperature, blood pressure, and pulse rate, height, weight, and waist circumference.
- b) The HIV Dementia Scale will be performed.
- c) 45 mL of blood and 15 mL of urine will be collected by standard methods. 15 mL of cerebrospinal fluid (CSF) will be collected by lumbar puncture using aseptic technique and an atraumatic needle.
- d) The following laboratory tests will be performed:
 - i) HIV RNA in blood plasma
 - ii) HIV RNA in CSF
 - iii) CSF total leukocyte count and differential, CSF erythrocyte count, CSF total protein, CSF albumin, CSF glucose
 - iv) For women of childbearing potential: Serum or urine pregnancy test.
- e) 5 mL of blood serum, 10 mL of blood plasma, 5 mL of whole blood, 5 mL of urine, and 8 mL of CSF

will be stored at -80C. An aliquot of peripheral blood mononuclear cells will be stored at -150C.

f) A three-week supply of Stribild will be dispensed from the research pharmacy.

On-Treatment Evaluations

- 4) Two-Week Assessment: Subjects will return at day 14 (one-week window) for safety and pharmacokinetic assessments that will include:
- a) Brief, safety-focused clinical assessment:
 - i) Vital signs including temperature, blood pressure, and pulse rate.
 - ii) A medical history assessment including symptoms and signs of adverse reactions
 - iii) Study drug adherence assessment
 - iv) For women of childbearing potential: serum or urine pregnancy screen.
- b) 75 mL of blood and 15 mL of urine will be collected by standard methods. 15 mL of CSF will be collected by lumbar puncture using aseptic technique and an atraumatic needle. Collection will follow a specific schedule as detailed in detailed in the *PK Sample Collection and Processing Document* and summarized in section 4.2.2 of the Master Protocol.
- c) The following laboratory evaluations will be performed:
 - i) Hematology: hemoglobin, hematocrit, mean corpuscular volume (MCV), white blood cell count, differential white blood cell count, and platelet count.
 - ii) Blood chemistries: electrolytes, blood urea nitrogen (BUN), creatinine, glucose, phosphorus, and calcium.
 - iii) Liver function tests: total bilirubin, AST, ALT, alkaline phosphatase, and albumin.
 - iv) Urinalysis, including urine glucose and protein
 - v) Estimated glomerular filtration rate (eGFR)
 - vi) For women of childbearing potential: Serum or urine pregnancy test.
 - vii) HIV RNA in blood plasma
 - viii) HIV RNA in CSF
 - ix) CSF total leukocyte count and differential, CSF erythrocyte count, CSF total protein, CSF albumin, CSF glucose
 - x) Lymphocyte subsets in blood (including CD4+ and CD8+ T-cell absolute counts and percents)
- d) Pharmacokinetics: Detailed instructions for performing the pharmacokinetic studies are detailed in the *PK Sample Collection and Processing Document*. Briefly:

StribildTM containing elvitegravir (EVG) 150 mg will be administered in the morning after breakfast, *e.g.* 9:00 am, for study days 1-14. The precise times of dosing on days 11, 12 and 13 will be recorded.

On the morning of study day 14, subjects will hold their morning dose and will report to the clinical research center at approximately 8:00 a.m. An indwelling catheter will be placed in one arm of the subject for serial PK sampling. StribildTM will be administered later that morning immediately after a meal and the precise time of drug administration will be recorded.

Blood samples will be collected prior to StribildTM dosing, and at 2, 4, and 6 hours following StribildTM administration. The catheter will then be removed and a lumbar puncture will be performed within 1 hour of the last blood sampling (\sim 7 hours after StribildTM dosing). Subjects will then be discharged from the clinical

research center.

- e) Drug dispensing: Six additional weeks of study drug will be dispensed from the research pharmacy.
- f) Specimen storage: In addition to specimens collected for the required PK assays, 5 mL of blood serum, 10 mL of blood plasma, 5 mL of whole blood, 5 mL of urine, and 8 mL of CSF will be stored at -80C.

5) Events Between Week 2 and Week 24 Visits

- a) The study coordinator will call study subjects at Weeks 8 and 16 (and more often at their discretion) to inquire about signs or symptoms of adverse effects as well as medication adherence. Results will be recorded on a CRF. If any symptoms are reported, the subject will be asked to come to the clinic to be evaluated by the study nurse and investigator (see Section 6.6 of the master protocol).
- b) Drug dispensing: Eight weeks of study drug will be dispensed at Weeks 8 and 16.
- c) HIV RNA in plasma: Study subjects will be asked to return to their primary care provider to obtain a measurement of HIV RNA in blood plasma per routine clinical care. This is anticipated to occur after approximately 12 weeks of treatment. Study subjects will be asked to bring a copy of the lab report to the research center. Alternatively and with the consent of the study subject, the research nurse will obtain the value from the clinic.

6) Week 24 Assessments

- a) A complete medical history and physical examination will be performed:
 - i) Prior diagnoses including liver disease, renal disease, fracture, osteoporosis, allergies, drug reactions, and most recent menses.
 - ii) Current symptoms including those of an active systemic illness (e.g., fever) and bleeding or easy bruising.
 - iii) Prescription and non-prescription medications taken within 14 days prior to entry.
 - iv) Vital signs, including temperature, blood pressure, and pulse rate, height, weight, and waist circumference.
- b) The HIV Dementia Scale will be performed.
- c) 75 mL of blood and 15 mL of urine will be collected by standard methods. 15 mL of cerebrospinal fluid (CSF) will be collected by lumbar puncture using aseptic technique and an atraumatic needle. Collection will follow a specific schedule as detailed in detailed in the *PK Sample Collection and Processing Document* and summarized in section 4.2.2 of the master protocol.
- d) The following laboratory tests will be performed:
 - i) Hematology: hemoglobin, hematocrit, mean corpuscular volume (MCV), white blood cell count, differential white blood cell count, and platelet count.
 - ii) Blood chemistries: electrolytes, blood urea nitrogen (BUN), creatinine, glucose, phosphorus, and calcium
 - iii) Liver function tests: total bilirubin, AST, ALT, alkaline phosphatase, and albumin.
 - iv) Coagulation: prothrombin time, international normalized ratio, partial thromboplastin time

- v) Urinalysis, including urine glucose and protein
- vi) Estimated glomerular filtration rate (eGFR)
- vii) For women of childbearing potential: Serum or urine pregnancy test.
- viii) HIV RNA in blood plasma
- ix) HIV RNA in CSF
- x) CSF total leukocyte count and differential, CSF erythrocyte count, CSF total protein, CSF albumin, CSF glucose
- xi) Lymphocyte subsets in blood (including CD4+ and CD8+ T-cell absolute counts and percentages)
- e) Pharmacokinetics: Detailed instructions for performing the pharmacokinetic studies are detailed in the *PK Sample Collection and Processing Document*. Briefly:

StribildTM containing elvitegravir (EVG) 150 mg will be administered in the morning after breakfast, *e.g.* 9:00 am, for study days 1-14. The precise times of dosing on days 11, 12 and 13 shall be recorded.

On the morning of study day 14, subjects will be instructed to hold their morning dose and will report to the clinical research center at approximately 8:00 a.m. An indwelling catheter will be placed in one arm of the subject for serial PK sampling. StribildTM will be administered later that morning immediately after a meal and the precise time of drug administration will be recorded.

Blood samples will be collected prior to StribildTM dosing, and at 2, 4, and 6 hours following StribildTM administration. The catheter will then be removed and a lumbar puncture will be performed within 1 hour of the last blood sampling (~ 7 hours after StribildTM dosing). Subjects will then be discharged from the clinical research center.

- f) 5 mL of blood serum, 10 mL of blood plasma, 5 mL of whole blood, 5 mL of urine, and 8 mL of CSF will be stored at -70°C. An aliquot of peripheral blood mononuclear cells will be stored at -150°C.
- g) Subjects will be strongly encouraged to have an appointment with a primary care provider scheduled within a week prior to the final study visit to obtain a prescription and allow for clinical dispensing of continuing antiretroviral therapy.

Premature Discontinuation

Subjects who prematurely discontinue study treatment will undergo an assessment similar to the one detailed for Week 24 with the following exceptions.

- a) The visit will not include lumbar puncture.
- b) The visit will not include PK assessment.
- c) The visit will not include drug dispensing.
- d) Following up with a primary care provider will be discussed with the study subject.

Off-Drug Requirements

Additional safety monitoring and reporting of Serious Adverse Experiences (SAEs) continues to be required upon completion or discontinuation of study treatment regardless of whether a protocol follow-up period is scheduled to occur. Adverse experiences occurring during the immediate 8-week period after the last dose of study treatment which meet SAE Reporting Requirements must be reported to the sponsor and the Institutional Review Board (IRB). If the study subject discontinues study treatment, after 8 weeks OFF study treatment,

there are 4 types of events which must be reported to the sponsor and the IRB if the relationship to the study treatment is assessed by the site physician as definitely, possibly, or unable to judge: DEATHS, NEW ONSET CANCERS, CONGENITAL ANOMALIES, PERMANENT DISABILITIES. The study nurse will call the study subject eight weeks after the last study visit to determine if an SAE has occurred.

STATISTICAL CONSIDERATIONS

General Design Issues

The first objective of this study is to evaluate the CSF pharmacokinetics of EVG. This will be accomplished by evaluating HIV-1 infected, treatment-naive subjects. In this single arm, open-label study, within-subject differences in pharmacokinetics parameters at week 2 and 24 will be analyzed, as each subject will serve as his/her own control. For the secondary objective, which is to evaluate the effect of StribildTM on the permeability of the blood-brain barrier and HIV Dementia Scores, we will consider within-subject differences in a similar manner to analyses for the primary objective.

Pharmacokinetic analysis

Two methods, one model-independent and one model-dependent analyses, will be undertaken in this study. The use of these two methods of analysis will serve as validation. For the model-independent method, total and unbound plasma concentrations and total CSF concentrations will be used to calculate a CSF/plasma ratio, based on individual subject concentration-time profiles. The model-dependent method will fit a population hierarchical mixed-effect model to the data including clinical outcomes. Relevant hypotheses can be tested using the likelihood ratio test. Individual pharmacokinetic parameters can be estimated by empirical Bayesian methods.

Endpoints

Primary endpoints

a) Plasma and CSF total/unbound concentrations of EVG over 2- and 24-week treatment periods

Secondary endpoints

- a) Proportion HIV RNA levels below the lower limit of quantitation in CSF and plasma from 2- and 24-week assessments.
- b) Changes in CD4+ T-cells at baseline and week 24.
- c) Changes in blood-brain-barrier permeability as indicated by CSF-to-serum albumin ratio between baseline and either week 2 or week 24.
- d) Changes in HIV Dementia Scale scores between baseline and week 24.

Sample Size and Accrual

Based on estimates from ING116070, assuming within-subject coefficients of variation between 30 and 40%, with a type I error of 0.05 and 90% power, a sample size of 14 would be sufficient to detect a minimum of 50% change in the CSF concentration of EVG using a two-sided paired t-test.

Any subject who prematurely discontinues study participation prior to completing at least one on-treatment PK assessment will be replaced by another subject.

Drug Regimens, Administration and Duration:

Days 1-14: Give StribildTM (150 mg EVG, po q AM)

Day 14: First PK assessment (PK1)

Days 15-168: Continue StribildTM (150 mg EVG, po q AM)

Day 168: Second PK assessment (PK2)

StribildTM (150 mg EVG, po q AM). With the exception of PK days, can be administered as a single dose in the morning, immediately after breakfast.

At PK assessment visits, subjects will be asked to hold all study drugs. Doses will then be administered in the clinical research center under direct observation by study staff.

Drug Formulations

a. StribildTM (150 mg elvitegravir, 150 mg cobicistat, 200 mg emtricitabine, and 300 mg tenofovir disoproxil fumarate): green, capsule-shaped, film-coated tablets. Store at room temperature (15-30 °C) (59-86 °F)

Drug Supply, Distribution and Pharmacy

Dispensing and monitoring drug-taking behavior

a. Adherence will be self-reported and documented by project staff on appropriate CRFs. Subjects will be asked to bring medication bottles to each visit.

Study supply acquisition

a. The study treatment will be supplied by Gilead Sciences to each study site and will then be dispensed by each site's research pharmacy.

Accountability

- a) The study pharmacist will maintain complete records of all study medications received and subsequently dispensed.
- b) All unused study medication will be returned to the study pharmacy and discarded following standard operating procedure.

Concomitant Medications

Precautions

a) STRIBILD is NOT recommended for coadministration with: emtricitabine or tenofovir DF (ATRIPLA, COMPLERA, EMTRIVA, TRUVADA, VIREAD); products containing lamivudine (COMBIVIR, EPIVIR, EPIVIR-HBV, EPZICOM, TRIZIVIR) or adefovir dipivoxil (HEPSERA); or ritonavir (NORVIR, KALETRA).

Contraindications

a) Coadministration of STRIBILD is contraindicated with drugs that are highly dependent on CYP3A for clearance and for which elevated plasma concentrations are associated with serious and/or life-threatening events, *e.g.* alfuzosin, rifampin, ergo derivatives, cisapride, St. John's wort, lovastatin, simvastatin, sildenafil, triazolam, oral midazolam. Specific case-by-case exemptions may be considered by the study investigators.

Management of Selected Toxicities

New Onset or Worsening Renal Impairment

a) Renal impairment, including acute renal failure and Fanconi syndrome, has been reported with the use of STRIBILDTM. If renal impairment occurs as indicated by a decrease of estimated creatinine clearance below 50 mL/min, study treatment will be discontinued. Subjects will be followed off treatment with evaluations as per section 4.2 of the master protocol.

Lactic Acidosis/Severe Hepatomegaly with Steatosis

a) Lactic acidosis and severe hepatomegaly with steatosis, including fatal cases, have been reported with the use of tenofovir DF, a component of STRIBILD, in combination with other antiretrovirals. Treatment with STRIBILD should be suspended in any subject who develops clinical or laboratory findings suggestive of lactic acidosis or pronounced hepatotoxicity.

Bone Effects, Fat Redistribution, and Immune Reconstitution Syndrome

- a) Decreases in bone mineral density, redistribution/accumulation of body fat, and immune reconstitution syndrome have been reported in patients treated with STRIBILDTM, which may necessitate further evaluation and treatment.
- b) Any Grade 2 or higher symptoms or laboratory abnormalities will result in termination of the subject from the study (see Section 4.2 of the master protocol for post-treatment evaluations).
- c) If a subject discontinues the study drugs prior to the pharmacokinetic sampling on day 14, s/he will be replaced in the original sample size.

Criteria for Treatment Discontinuation

- a) The subject or legal guardian refuses further treatment and/or follow-up evaluations.
- b) The investigator determines that further participation would be detrimental to the subject's health.
- c) The subject fails to comply with the study requirements so as to cause harm to self or seriously interfere with the validity of the study results.
- d) The subject requires treatment with medications that are disallowed while on this study (Section 6.5.2 of the master protocol).
- e) Drug toxicity as defined in Section 6.6 of the master protocol.
- f) Pregnancy.

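### The Week 24 PK text repeats Day 14 day numbers and an entry-based medication look-back, so as written it does not ask for dose times before PK2 (low severity)

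*Combined protocol and SAP*

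**What the plan says.** All places are in Section 9 of the combined document.

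- **Two-Week Assessment, Pharmacokinetics:** morning dosing on study days 1-14, a held dose on day 14, and "The precise times of dosing on days 11, 12 and 13 will be recorded".
- **Week 24 Assessments, Pharmacokinetics:** nearly the same paragraph, including "The precise times of dosing on days 11, 12 and 13 shall be recorded" and "On the morning of study day 14, subjects will be instructed to hold their morning dose".
- **Drug Regimens, Administration and Duration:** "Day 168: Second PK assessment (PK2". The schedule of assessments gives days 161-175 for Week 24.
- **Week 24 history:** "Prescription and non-prescription medications taken within 14 days prior to entry", worded as in the Baseline (Entry) Evaluation.
- **Week 2 visit window:** days 12-20 in the schedule of assessments, but in the text "Subjects will return at day 14 (one-week window".
- **Week 2 clinical assessment:** the text lists "A medical history assessment including symptoms and signs of adverse reactions" and "Study drug adherence assessment", with no medication item. The schedule marks a brief assessment at both Screening and Week 2, and the brief history at Screening does include medications.

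Both PK paragraphs present themselves as brief summaries of a PK Sample Collection and Processing Document. The visit text also refers to section 4.2.2 of the master protocol. Neither was supplied.

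**The concern.** The Week 24 instruction is explicit, and it points to the wrong period. It asks for the dose times before the first PK visit (PK1) under the heading of the second.

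A pre-dose plasma concentration depends directly on when the previous dose was taken. Plasma and CSF concentrations together form the primary endpoint. General Design Issues plans a within-subject comparison of Week 2 with Week 24, and the pharmacokinetic analysis fits a population mixed-effect model. For that model, a wrong or assumed preceding dose time becomes error in the trough at PK2. A missed dose may show in adherence reports or in the profile, but the clock time of a late dose cannot be recovered from either.

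The medication item has the same fault on a smaller scale: the question is asked at Week 24, but its look-back is anchored to entry.

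**Working it through.** **Plan's own figure.** The plan gives none on this point. Its sample-size statement (14 subjects, 50% change, within-subject CV 30-40%, 90% power, two-sided 0.05) serves only as a scale. It reproduces by normal approximation at CV 40%, taking the SD of the difference as CV × √2: ((1.960 + 1.282) × 0.40 × 1.414 / 0.50)² = 13.4, rounded up to 14.

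**Day arithmetic.**
- PK2 on Day 168: 168 − 13 = 155 and 168 − 11 = 157 days after the recorded doses.
- Over the window 161-175: from 161 − 13 = 148 to 175 − 11 = 164 days.
- The 14 days before entry (day 0) lie 168 to 182 days before Day 168.

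Neither look-back reaches the days before PK2.

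**Effect of an unrecorded late dose.** Assumptions: one compartment, once-daily dosing at steady state, plasma half-life h of 3, 6, 9 or 12 h, and the dose before the visit taken 2 h late. Let r = 2^(−24/h).

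- Pre-dose ratio = [2^(−22/h) + r²/(1 − r)] / [r/(1 − r)], so the change is (1 − r)(2^(2/h) − 1).
- After the observed dose, relative plasma change = r(1 − r)(2^(2/h) − 1).

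| h (h) | r | 2^(2/h) | Pre-dose plasma | Plasma at about 7 h |
|---|---|---|---|---|
| 3 | 0.0039 | 1.587 | +59% | +0.2% |
| 6 | 0.0625 | 1.260 | +24% | +1.5% |
| 9 | 0.157 | 1.167 | +14% | +2.2% |
| 12 | 0.250 | 1.122 | +9% | +2.3% |

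**CSF at 7 h.** Add a plasma-CSF link with an assumed equilibration half-life q of 0.5, 1, 2, 4, 8 or 12 h. Each dose contributes f(t) = e/(e − k) × (exp(−kt) − exp(−et)), with k = ln2/h and e = ln2/q (k·t·exp(−kt) when e = k), summed over 40 daily doses at t = 7 + 24n. The late dose enters at t = 29 instead of 31. The grid runs from +0.2% to +3.8%.

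The largest value is at h = 6, q = 8, where f(t) = 3 × (2^(−t/8) − 2^(−t/6)). There f(29) = 0.1379, f(31) = 0.1210 and the total is 0.4440, so the change is (0.1379 − 0.1210)/0.4440 = 3.8%. One such subject moves a mean percentage change over 14 subjects by 3.8/14, or about 0.3 points.

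**PK1.** For a visit on day d, compare {d − 3, d − 2, d − 1} with {11, 12, 13}. For d = 12 to 20 the overlap is 1, 2, 3, 2, 1, 0, 0, 0, 0. All three doses match on 1 of 9 allowed days (day 14). The immediately preceding dose is covered on 3 of 9 (days 12-14), and none of the three on 4 of 9. If the one-week window means plus or minus 3 days (an assumption; days 11-17), the counts are 1, 3 and 2 of 7. These count allowed days; they are not visit probabilities.

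**The case against.** The strongest reply is that the paragraph is a declared summary, and the separate PK document may ask for the right dose times. That limits the claim to the supplied text: nobody can say from these documents that the PK2 dose times will go unrecorded. It does not remove the contradiction between study day 14 and Day 168.

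Much of the visit is already covered. The Drug Regimens text applies the hold and observed dosing to every PK visit, and the Week 24 text records the visit-day dose time. Adherence is self-reported on case report forms, bottles come to each visit, and the Week 8 and 16 calls ask about adherence. A reader might infer that adherence is not assessed at Week 24 because its list omits the item; the general provision answers that. None of these sources gives the times of the doses before PK2.

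A reader might also infer that medications are not asked about at either PK visit. The documents do not support that. The Week 24 item exists and only its anchor is wrong. The schedule marks at Week 2 the same brief assessment that covers medications at Screening. Section 15 also stops study drug for prohibited co-medication, which presupposes that it is ascertained. What remains for Week 2 is a mismatch between schedule and text.

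Finally, days 11-13 naturally mean the three days before a nominal Day 14. That is fair, but the allowed window is wider than that day.

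**Conclusion.** The Week 24 PK day references and medication anchor are wrong as written, at low severity. The consequence falls mainly on pre-dose plasma at PK2 and on the population model: +59% down to +9% for a dose 2 h late, under assumed half-lives of 3 to 12 h and a one-compartment model. For that late dose, plasma at about 7 h changes by at most 2.3% and CSF by at most about 4%, in the affected subject only.

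A reader might conclude that the Week 2 versus Week 24 CSF comparison is at risk, perhaps by setting a missed dose in one subject against the 50% change used for sample size. That does not follow. The 50% is a mean paired change in 14 subjects, and a missed dose may be recognised from adherence reports or the profile. The CSF effect of a late dose is small beside the 30-40% within-subject CV.

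The day arithmetic is certain. The percentages rest on assumed half-lives and model form, and whether the information is really lost depends on documents not supplied.

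**What to change.** First check the PK Sample Collection and Processing Document and master protocol section 4.2.2. If they already ask for these items, only the wording here needs aligning. Otherwise:

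1. Reconcile the day references in the Week 24 PK paragraph with Day 168 and the schedule window, and reconcile the two statements of the Week 2 window.
2. At each PK visit, replace the fixed days 11-13 with an instruction to record the clock times of the three doses that precede that visit.
3. Anchor the Week 24 medication look-back to the 14 days before that visit, and align the Week 2 list with the brief assessment marked in the schedule.

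The cost is wording and a few case report form fields, with no extra visit, tube or catheter time. No change to dosing, the hold or the sampling times is proposed.
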